## **7.1 Pre-Treatment-Emergent Events**

Prometheus considers AEs that occur between the time the subject signs the informed consent form for the study and the time when that subject is first administered the study drug as “pre-treatment-emergent” AEs. Any pre-treatment-emergent event will be recorded as an AE but will be clearly documented as pre-treatment emergent event in the data listings.

## 7.2 Laboratory Abnormalities as Adverse Events

Many laboratory abnormalities observed during the course of a study will be included under a reported AE describing a clinical syndrome (e.g., elevated BUN and creatinine in the setting of an AE of renal failure, or decreased hemoglobin in a case of bleeding esophageal varices). In such cases, the laboratory abnormality itself (e.g., elevated creatinine in a setting of renal failure) does not need to be recorded as an AE. However, isolated laboratory abnormalities should be reported as AEs if they are considered to be clinically significant by the Investigator. Criteria for a “clinically significant” laboratory abnormality are:

- a) A laboratory abnormality that leads to a dose-limiting toxicity (e.g., an abnormality that results in study drug dose reduction, suspension or discontinuation), or
- b) A laboratory abnormality that results in any therapeutic intervention (i.e., concomitant medication or therapy), or
- c) Other laboratory abnormality judged by the Investigator to be of any particular clinical concern (e.g., significant fall in hemoglobin not requiring transfusion)

For laboratory abnormalities that do not meet the above criteria but are outside of normal range (e.g., < or > normal reference range), the Investigator should indicate whether the value is clinically significant (CS) or not clinically significant (NCS) for the subject.

## 7.3 Grading/Severity of Adverse Events

The Investigator must define the severity of each AE using the NCI’s CTCAE Version 5.0. A severity category of mild, moderate, severe, life threatening, or death as defined in Table 6 must be entered on the AE eCRF. The Investigator will consider the range of the possible severity of the event and identify the severity that is the most appropriate according to her/his medical judgment.

**Table 6 Severity of Adverse Events**

Grade	Clinical Description of Severity
1	Mild; asymptomatic or mild symptoms; clinical or diagnostic observations only; intervention not indicated.
2	Moderate; minimal, local or noninvasive intervention indicated; limiting age-appropriate instrumental ADL*.
3	Severe or medically significant but not immediately life-threatening; hospitalization or prolongation of hospitalization indicated; disabling; limiting self care ADL**. Note: An experience may be severe but may not be serious, e.g., severe headache).
4	Life-threatening consequences; urgent intervention indicated.
5	Death related to AE.

A Semi-colon indicates ‘or’ within the description of the grade.

Note: Activities of Daily Living (ADL):

\*Instrumental ADL refer to preparing meals, shopping for groceries or clothes, using the telephone, managing money, etc.

\*\*Self care ADL refer to bathing, dressing and undressing, feeding self, using the toilet, taking medications, and not bedridden.

## **7.4 Relationship of Adverse Events**

### **7.4.1 Relationship of Adverse Events to Study Drug Administration**

The Investigator will determine if there is a reasonable causal relationship between the study drug and an AE or not. The Investigator will use her/his best medical judgment and consider all relevant factors (e.g., temporal relationship, location of the event, the subject's relevant medical history, concomitant therapies, and concurrent conditions) to determine the relationship of the AE to the study drug. The Investigator will define the relationship of an AE to the study drug by selecting one of the following categories:

**Related:** There is a reasonable possibility that there is a causal relationship between the study drug and the AE.

**Not Related:** There is not a reasonable possibility that there is a causal relationship between the study drug and the AE.

The term "reasonable causal relationship" means there are facts or arguments to suggest a causal relationship (International Conference on Harmonisation (ICH) E2A).

### **7.4.2 Relationship of Adverse Events to Study Procedures**

Relationship (causality) to study procedures should be determined for all pre-treatment-emergent events and AEs. The relationship should be assessed as Related if the Investigator considers that there is reasonable possibility that an event is due to a study procedure. Otherwise, the relationship should be assessed as Not Related.

## **7.5 Recording and Reporting of Adverse Events**

### **7.5.1 Recording Adverse Events**

All AEs will be recorded in the appropriate section of the eCRF. Subjects withdrawn from the study due to AEs will be followed by the Investigator until the outcome is determined and, when appropriate, additional written reports and documentation will be provided. The Investigator should attempt, if possible, to establish a diagnosis based on the presenting signs and symptoms.

If the AE meets the definition of an SAE, or if the Investigator becomes aware of an unexpected AE event that places the subject at risk, or if there is a pregnancy at any time after the study drug administration up to the end of the study follow-up period, the event must be documented and reported.

### 7.5.2 Investigator Reporting of a Serious Adverse Event

In agreeing to the provisions of this protocol, the Investigator accepts all legal responsibilities for prompt notification of serious adverse events (SAEs) to [REDACTED] CCI. The Investigator (or designee) is required to complete the SAE page in the eCRF enabling transmission to [REDACTED] CCI using the electronic data capture (EDC) system. In the event EDC transmission is not possible, (e.g., there are access or system problems), then the Investigator (or designee) must report the SAE to [REDACTED] CCI by emailing or faxing a completed paper SAE form to:

Fax: PPD [REDACTED]  
Email: PPD [REDACTED]

All SAEs must be reported to [REDACTED] CCI within 24 hours after the Investigator recognizes/classifies the event as a SAE.

The initial SAE report should include at a minimum: subject number, a narrative description of the event, and an assessment by the Investigator of the intensity of the event and relationship of the event to study drug. The initial SAE report received from the site should be as complete as possible. A complete follow-up SAE report must be submitted when information not available at the time of the initial report becomes available. The Sponsor (or designee) may request SAE follow-up information. Copies of any relevant data from the hospital notes (e.g., ECGs, laboratory tests, discharge summary, postmortem results) should be sent to the addressee, if requested.

The Investigator must receive acknowledgement by [REDACTED] CCI that the information about the SAE has been received. In the event that the Sponsor or designee permits an alternate delegate, the Investigator and staff will be notified and provided the alternate's contact information.

The Investigator is responsible for continuing to report to the [REDACTED] CCI any new or relevant follow-up information that he/she learns about the SAE.

### 7.5.3 Investigator Reporting of a Pregnancy

Investigator (or designee) should notify [REDACTED] CCI of all pregnancies occurring after start of study drug and 12 weeks after last dose in enrolled female subjects or the female partner of male subjects.

If a pregnancy occurs, a Pregnancy Report Form should be completed by the Investigator (or designee) and submitted to [REDACTED] CCI via fax to PPD [REDACTED], or by email to PPD [REDACTED].com within 24 hours after learning of the pregnancy.

Female subjects who become pregnant must discontinue study drug, and the Investigator should evaluate the risks and benefits of continuing with the study after discussing the risks of the pregnancy and possible effects on the fetus with the subject. A determination regarding study drug discontinuation will be made for male subjects with a partner pregnancy based on risks involved by the Investigator and/or Sponsor.

Pregnancy is not regarded as an AE unless there is a suspicion that study drug may have interfered with the effectiveness of a contraceptive medication.

The outcome of all pregnancies (spontaneous miscarriage, elective termination, normal birth, or congenital abnormality) must be followed up and documented even if the subject was discontinued from the study. Female partners of male subjects are asked to sign a separate partner pregnancy informed consent form in order to collect pertinent personal and medical information regarding the status and outcome of the pregnancy.

All reports of congenital abnormalities/birth defects are considered SAEs and should be reported per [Section 7.5.2](#). Spontaneous miscarriages should also be reported and handled as SAEs. Elective abortions without complications should not be handled as AEs unless they were therapeutic abortions. The medical reason (e.g., fetal disease) for therapeutic abortion will be reported as an SAE.

## 7.6 Additional Investigator Responsibilities for Serious Adverse Events

The Investigator and supporting personnel responsible for subject care should discuss with the Medical Monitor any need for supplemental investigations of SAEs. The results of these additional assessments conducted must be reported to the Sponsor. If a subject dies during participation in the study and a post-mortem examination is performed, a copy of the autopsy report must be submitted to Sponsor or designee.

## 7.7 Post-Study Follow-Up of Adverse Events

All AEs, including a worsening of clinically significant laboratory values or physical examination findings compared with baseline values, must be followed until the event resolves, the condition stabilizes, the event is otherwise explained, or the subject is lost to follow-up.

AEs ongoing at the final visit will be followed for as long as necessary to adequately evaluate the subject's safety or until the event stabilizes or resolves. If resolved, a resolution date should be documented on the eCRF or reported to Sponsor or designee if the eCRFs have been collected. The Investigator is responsible to ensure that follow-up includes any supplemental investigations as may be indicated to elucidate the nature and/or causality of the AE. This may include additional laboratory tests or investigations, histopathological examinations, or consultation with other health care professionals as is practical.

## 7.8 Notification of Post-Study Serious Adverse Events

Investigators are not obligated to actively follow subjects after the completion of the study. However, if the Investigator becomes aware of an SAE, he/she should notify [REDACTED] if such events are attributable to the study drug. The notification to [REDACTED] of a post-study SAE by the Investigator should occur within 24 hours of becoming aware of the SAE.

## 7.9 IRB/IEC Notification of Serious Adverse Events

The Investigator is responsible for promptly notifying her/his IRB/IEC of all SAEs, including any follow-up information, occurring at her/his site and any SAE regulatory report, including any follow-up reports that he/she receives from the Sponsor or designee.

## 7.10 Health Authority Safety Reports

Prometheus or its representatives will submit a safety report to appropriate regulatory agencies, for all suspected unexpected serious adverse reactions (SUSARs) and any other applicable SAEs to regulatory authorities in accordance with national regulations in the countries where the study is conducted. SUSARs will be submitted to the regulatory authorities as expedited report within 7 days for fatal and life-threatening events and 15 days for other serious events, unless otherwise required by national regulations. Prometheus or its representatives will also prepare and distribute an expedited report for other safety issues which might alter the current benefit-risk assessment of the study drug or impact the overall conduct of the trial. Prometheus or its representatives will send copies of each safety report submitted to the regulatory agencies to the Investigators who are actively participating in Prometheus-sponsored clinical studies. Safety reports must be submitted to the appropriate IRB/IEC according to local regulations and guidelines. Documentation of the submission to the IRB/IEC must be retained for each safety report.

## 7.11 Data Monitoring Committee (DMC)

Prometheus will establish an independent DMC for PRA023 to oversee the benefit-risk profile in IBD and safety across the entire program. The DMC will review safety data at periodic intervals from this and all other PRA023 studies conducted by Prometheus Biosciences. Members of the DMC will not be allowed to participate as Investigators in any of the PRA023 studies.

A charter, which will include a detailed description of the scope and the extent of its responsibilities and procedures, will be implemented prior to any data review. The charter will specify how the data will be provided to the committee member (e.g., blinded, unblinded, grouped or not, etc.) for review. These documents (charter, open and closed meeting minutes, etc.) will be considered part of the study documentation, but not of this protocol. The DMC will review data within its general remit to oversee subject safety for the PR200 program and provide recommendations and guidance to the Sponsor in accordance with the procedures stated in its charter.

A formal DMC monitoring meeting will occur **prior** to the commencement of this study, where the DMC will assess all available safety data from the normal healthy volunteer study (Study PR200-101). This study will commence following the demonstration of acceptable safety profile of PRA023 at a dose of  $\geq 500$  mg in multiple ascending dose study in Study PR200-101.

All Investigators, responsible IRB/IECs, and applicable regulatory agencies will be informed of any decisions made by Prometheus Biosciences based on recommendations from the DMC relating to subject safety and affect the conduct of this study. The Investigators will inform the subjects of such actions and the protocol and ICF will be revised, as appropriate.

## 8 ASSESSMENT OF STUDY VARIABLES

The data will be analyzed by Prometheus or an official designee (e.g., a contract research organization [CRO]).

### 8.1 Randomization

This is an open-label study where all subjects will receive PRA023. Eligible subjects will be assigned a subject randomization number by the IRT system at Week 0/Day 1 upon confirmation of study eligibility as a means to track the number of eligible subjects enrolled in the study. Subjects who are re-randomized in OLE will retain their original subject numbers.

### 8.2 Justification of Sample Size

The planned sample size is 50 subjects, which will provide a statistical power of 80% to test against the null hypothesis of endoscopic improvement rate of 12%, at 1-sided significance level of 0.025, assuming the endoscopic improvement rate for PRA023 is 27%.

The null hypothesis of an endoscopic improvement (decrease in SES-CD  $\geq$  50%) rate of 12% is based on a meta-analysis estimate of the upper limit of 95% CI of the observed placebo rate (95% CI) of 9.5% (7.1, 11.9) from multiple modern-era CD clinical trials with centrally read endoscopy and similar eligibility criteria ([Table 7](#)).

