**Table 7 Placebo Endoscopic Response Rates in Recent CD Clinical Trials**

Clinical Trial	N	Placebo Endoscopic Response Rate (%)
Feagan et al. 2017	39	13
Vermeire et al. 2017	44	14
Sands et al. 2019	64	10.9
Selinger et al. 2018	59	3.4
Advance Study 2021	175	12
Motivate Study 2021	187	11
Average		10.7
Sample-size Weighted Average	568	9.5

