#### **9.2.2 Evaluation of Efficacy Parameters**

The primary efficacy endpoint, endoscopic improvement at Week 12, will be used to assess the efficacy of PRA023. The proportion of subjects in the per-protocol population with endoscopic improvement at Week 12 will be tested against the null hypothesis of 12%, an observed placebo

rate from multiple CD trials. Chi-square test will be used with a 1-sided significance level of 0.025. If significant, the 1st secondary endpoint of proportion of subjects in FAS achieving clinical remission will be tested against the null hypothesis of clinical remission rate of 16% (an observed remission rate for the placebo treated patients from multiple CD trials ([AbbVie 2021](#), [Feagan 2017](#), [Sands 2019](#), [Selinger 2018](#), [Vermeire 2017](#))).

The point estimates for the primary and secondary endpoints will be calculated along with 95% confidence interval for FAS and by CDx status (CDx+ or CDx-).

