1 INTRODUCTION

This statistical analysis plan (SAP) describes in detail the analyses to be performed for the Induction Period (IP) of the study on the safety, efficacy, and pharmacokinetics of PRA023 in subjects with moderately to severely active Crohn’s Disease(CD). This SAP describes the statistical analysis methods and data presentations to be used in tables, figures, and listings (TFLs) in the clinical study report (CSR) for study PR-200-103. This SAP is based on the study protocol version 3.0.

There will be a primary analysis after all subjects have completed 12-week IP. The analysis will include complete data for the induction period and interim data for the OLE as of the cutoff date for the database lock. Outstanding data queries would have been resolved or adjudicated as unresolvable, and data should have been cleaned and finalized before database lock. Following the database lock after all subjects have completed Induction Period, the primary analysis of the data will be performed.

The SAP will be finalized and approved before 50% of planned subjects enrolled and initiated dosing. Any changes made after the finalization and approval of the SAP will be documented in the CSR with the rationale.

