5.6 PROTOCOL DEVIATIONS

Review of all protocol deviations will be performed on an ongoing basis during the conduct of the study. The number and percentage of subjects with major protocol deviations will be summarized. Subjects with important protocol deviations will be excluded from PP Analysis Set. The important protocol deviation could include, but are not limited to:

- Major protocol deviation related to certain study eligibility
 - Entry criteria that would impact on efficacy analyses: Inclusion criteria 2,3,or 4
- Major protocol deviation related to study treatment
 - Receiving incorrect investigated products, or
 - Missing ≥ 2 scheduled infusions during IP
- Unevaluable or missing Week 12 SES-CD score

A by-subject listing will be provided for those subjects with any protocol deviations before database lock. A separated by-subject listing will be provided for important protocol deviations that resulted in exclusion from the PP analysis set.

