6.2 PRIMARY EFFICACY ENDPOINT

The primary efficacy endpoint, endoscopic improvement at Week 12, will be used to assess the efficacy of PRA023. The proportion of subjects in PP analysis set with endoscopic improvement at Week 12 will be tested against the null hypothesis of 12%, an upper bound of observed placebo rate from multiple CD trials (Table below and Table 6 of study protocol).

Clinical Trial	N	Placebo Endoscopic Response Rate (%)
Feagan et al. 2017	39	13
Vermeire et al. 2017	44	14
Sands et al. 2019	64	10.9
Selinger et al. 2018	59	3.4
Advance Study 2021	175	12
Motivate Study 2021	187	11
Average		10.7
Sample-size Weighted Average	568	9.5
95% CI		(7.1, 11.9)

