6.2.1 PRIMARY ANALYSIS

The proportion of subjects with endoscopic improvement in PP analysis set will be estimated by the number of subjects who achieved the improvement at Week 12 divided by the total number of subjects in PP analysis set. The confidence interval for the proportion will be calculated using Wilson-score method (Wilson 1927). If the resulting lower bound of 95% CI is greater than 12%, the null hypothesis is, therefore, rejected at a 1-sided significance level of 0.025.

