6.2.2 SENSITIVITY ANALYSIS

In the sensitivity analysis, patients in FAS with missing SES-CD score at Week 12 will be considered as a non-responder for the endpoint of endoscopic improvement. The 95% confidence interval will then be calculated according to Wilson score method.

The proportion of subjects with endoscopic improvement for PP analysis set and associated 95% confidence intervals will also be estimated by the following subgroups:

- CDx status (CDx+ or CDx-)
- Number of prior biologic use (0, 1, or 2+)
- Disease extent (ileal only, colonic only, or both)
- Disease severity (baseline SES-CD ≤ 16, or > 16)
- Concomitant use of immunosuppressive including AZA, 6MP, and MTX (Yes, or No)
- Concomitant use of oral corticosteroids (Yes, or No)
- ADA status (positive, negative)

Given the small sample size of the trial, the results of subgroup analysis should be interpreted with caution. The forgoing analysis may be modified when the sample size in a subgroup is deemed too small.

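### The 9.5% placebo rate behind the 12% null is labelled a sample-size weighted average, but weighting by N gives 10.9% (8.3, 13.4); the pooling method behind the printed figure is not named

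*Protocol*

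**What the plan says.** Protocol 8.2 and SAP 3.2 set the null endoscopic improvement rate at 12% from a "meta-analysis estimate of the upper limit of 95% CI of the observed placebo rate (95% CI) of 9.5% (7.1, 11.9" per cent. Protocol 8.2 points to Table 7, which lists six placebo arms with N and rate, a simple average of 10.7, and a row headed "Sample-size Weighted Average" with N 568 and the value 9.5. The SAP 6.2 table repeats these rows and puts the 95% CI (7.1, 11.9) directly under the weighted row.

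The 12% is described in two ways. SAP 6.2 has "null hypothesis of 12%, an upper bound of observed placebo rate from multiple CD trials". Protocol 9.2.2 has "tested against the null hypothesis of 12%, an observed placebo" rate.

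SAP 6.2.1 makes 12% the success threshold for the Wilson interval in the per-protocol set: "If the resulting lower bound of 95% CI is greater than 12" per cent, the null is rejected at one-sided 0.025. Among the deviations that can remove a subject from that set, SAP 5.6 lists "Unevaluable or missing Week 12 SES-CD score", so the analysed N may differ from 50.

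**The concern.** The table's two other summary figures, the total of 568 and the simple average of 10.7, reproduce from the printed rows. The weighted row does not. Its label describes a calculation that gives a higher rate and a higher upper limit than those printed.

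The induction period has no control arm, so for the primary endpoint the historical 12% does the work that a placebo group would do. A reader who trusts the label will take 12% as the upper 95% limit of the N-weighted placebo rate. That limit is 13.4%. At N = 50 the two figures are one responder apart: 11 responders clear 12% but not 13.4%. What is at stake is whether the origin of the benchmark is described correctly, and how much certainty it implies about the margin over placebo.

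**Working it through.** **Inputs.** Protocol Table 7, repeated in SAP 6.2. The last four columns are computed.

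| Placebo arm | N | Rate p | N×p | Share of N | w = N/[p(1−p)] | Share of w |
|---|---|---|---|---|---|---|
| Risankizumab phase 2, 2017 | 39 | 13% | 5.07 | 6.9% | 344.8 | 5.1% |
| Filgotinib phase 2, 2017 | 44 | 14% | 6.16 | 7.7% | 365.4 | 5.4% |
| Mirikizumab phase 2, 2019 | 64 | 10.9% | 6.98 | 11.3% | 659.0 | 9.8% |
| Etrolizumab cohort 1, 2018 | 59 | 3.4% | 2.01 | 10.4% | 1796.4 | 26.7% |
| Advance, 2021 | 175 | 12% | 21.00 | 30.8% | 1657.2 | 24.6% |
| Motivate, 2021 | 187 | 11% | 20.57 | 32.9% | 1910.1 | 28.4% |
| Sum | 568 | | 61.78 | | 6732.9 | |

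**1. The plan's own figures.** The simple average is 64.3/6 = 10.7%, as printed. Fixed-effect inverse-variance pooling of the raw proportions gives Σwp/Σw = 637.9/6732.9 = 9.47%. Its standard error is 1/√6732.9 = 1.22 points, so the 95% CI is 7.09 to 11.86. With whole responder counts (5, 6, 7, 2, 21, 21) the result is 9.50% (7.11, 11.90). Both round to the printed 9.5% (7.1, 11.9).

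The interval alone does not identify the method, because a Wald interval around 9.5% with n = 568 also rounds to (7.1, 11.9). The identification rests on the point estimate.

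**2. The calculation named by the label.** ΣNp/ΣN = 61.78/568 = 10.88%. The Wald 95% CI is 10.88% ± 1.96 × √(0.1088 × 0.8912/568), which is 8.3% to 13.4%.

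**3. Rounding.** With the lowest unrounded rates that fit the table (12.5, 13.5, 10.85, 3.35, 11.5 and 10.5%), the N-weighted mean is 59.50/568 = 10.5%. Rounding cannot give 9.5%.

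**4. Why the two weightings differ.** Raw inverse-variance weights grow as p falls, so the arm at 3.4% carries 26.7% of the weight with 10.4% of the patients. Without that arm the same method gives 11.7% (8.9, 14.5).

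**5. Upper limits by method.**

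| Pooling method | Upper 95% limit |
|---|---|
| Inverse-variance, raw proportions | 11.9% |
| Freeman-Tukey | 13.2% |
| Arcsine | 13.3% |
| N-weighted (Wald) | 13.4% |
| DerSimonian-Laird | 13.4% |
| 62/568, Wilson | 13.7% |
| Logit | 14.2% |
| Log | 14.4% |

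**6. Effect on the decision rule at N = 50.** The Wilson lower limit is 12.75% for 11/50 and 14.30% for 12/50.

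| Benchmark | Responders needed | Exact power at 27% |
|---|---|---|
| 12% | 11/50 | 83.0% |
| 13.4% | 12/50 | 73.3% |

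The 11/50 rule succeeds 1.7% of the time at a true rate of 10.9%, 3.2% at 12% and 6.4% at 13.4%. For per-protocol sizes 40 to 55, moving the benchmark from 12% to 13.4% costs one responder at 14 of the 16 sizes, with power at 27% lower by 7.7 to 12.2 points. It costs none at N = 42 or N = 47.

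**The case against.** The strongest reply is that only a label is wrong. Protocol 8.2 and SAP 3.2 speak of a meta-analysis, inverse-variance pooling is a recognised form of one, and 9.5% (7.1, 11.9) reproduces under it. The 12% null lies above the N-weighted estimate (10.9%) and the simple average (10.7%), and the stated 80% power is met.

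Most of this stands. The meta-analysis wording is not shown to be false, and nothing here makes 9.5% an invalid estimate. But the only description of the weights in either document is the row label, and its own value contradicts it. The row also feeds the null for the primary endpoint, so it is more than a background figure.

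It can also fairly be said that 13.4% is one choice among several. The other methods tried give 13.2% to 14.4%, no document proposes 13.4% as a null, and any reader can set the Wilson interval against it. SAP 6.2.2 already adds a second interval, for the full analysis set: "The 95% confidence interval will then be calculated according to Wilson score method". A comparison with 13.4% is therefore optional.

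A reader might infer that the pooling method was picked to lower the benchmark, since it gives the lowest upper limit of those tried. The documents give no evidence of motive, and even the method is inferred.

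**Conclusion.** The row is wrong as labelled. The N-weighted placebo rate is 10.9% (8.3, 13.4), not 9.5% (7.1, 11.9): 1.4 points higher in the estimate and 1.5 points higher in the upper limit. The 12% null is the upper 95% limit only under a weighting that neither document names and that leans on one 59-patient arm. Protocol 9.2.2 adds to the confusion by calling an upper limit an observed rate.

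Three stronger readings are not supported:

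- **That 12% is too low or the success rule invalid.** It exceeds the N-weighted estimate, and at a true rate of 10.9% the 11/50 rule succeeds 1.7% of the time.
- **That the trial is underpowered.** Exact power is 83.0% at 27%. The 73.3% applies only if 13.4% is taken as the null.
- **That 12% is the only efficacy comparator.** It is the comparator for the primary endpoint; clinical remission is tested against 16%.

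The label error rests only on the printed N and rates. The inverse-variance source is an inference from matching figures. The power figures assume 50 analysed subjects.

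**What to change.** 1. In protocol Table 7 and the SAP 6.2 table, relabel the 9.5% row with the pooling method actually used, and add the true N-weighted row, 10.9% (8.3, 13.4).
2. In protocol 8.2 and SAP 3.2, name that method and state that the upper limit depends on it: 11.9%, against 13.4% under N-weighting.
3. In protocol 9.2.2, describe 12% as the upper 95% limit of the pooled placebo rate, in line with SAP 6.2.
4. Keep the 12% test and success rule unchanged.
5. Optionally, also report the primary Wilson interval descriptively against 13.4% (12/50 needed, power 73.3% at 27%), identified in the CSR as added after SAP V02. SAP 1 gives the route: "Any changes made after the finalization and approval of the SAP will be documented in the CSR with the rationale".

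The cost is wording in five places and a less favourable stated benchmark, with no extra patients. The protocol edits need an amendment with regulatory and IRB/IEC review (protocol 10.5) and can be bundled with the next one. SAP V02 is final, so its edits need a SAP amendment or an entry in the CSR. Because the primary threshold does not move, open-label access to the data does not compromise the primary test.
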